10.3. Sample Size Estimation for Powered Secondary Safety Endpoints

The total sample size required to meet the primary safety and effectiveness objectives is 262 subjects not accounting for attrition. The overall rate of device or procedure related adverse events in the IDE study is 14%. A conservative estimate of 20% is chosen to account for the additional follow-up time. Assuming an underlying rate of any device and/or procedure related adverse event of 20% in each group, a sample size of 112 per study group, for a total of 224 subjects is required to power for the assessment of the secondary safety endpoint.

Because the rates of revision/resurgery are expected to be less than the rates for the primary safety endpoint, the study is adequately powered for this objective as this endpoint utilizes the same non-inferiority margin as the primary safety endpoint.

10.4. Level of Significance and Power

All tests of significance will be performed at the two-sided 0.05 significance level (one-sided 0.025), unless otherwise specified. As both the primary effectiveness and safety objectives must be met for study success, no adjustment for multiplicity is required. Additionally, the powered secondary safety endpoints for (1) device and/or procedure related adverse events, and (2) revision or resurgery will be tested hierarchically in the order presented in the event the primary safety objective is met. Therefore, no adjustment for multiplicity is required.

10. Data Structure and Handling

11.1. Data Handling and Transfer

Programming of analysis datasets, tables, figures and listings will be conducted during the data management phase of the study. Tables, figures, and listings may be reviewed prior to final data lock for data review. Any data values requiring investigation or correction will be identified, and protocol deviations will be reviewed. The final run of outputs will take place after the data is deemed final.

11.2. Missing Data

The number and proportion of missing values at each observation period will be reported along with the reason for missing data, if known. Specific missing data handling procedures for each of the powered primary and secondary endpoints are presented in the endpoint analysis Section 12.6 below. No missing data handling procedures for the other secondary endpoints are pre-defined.

11.3. Visit Windows

All data attributed to a time point per the CRF will be included in the analysis of that time point, regardless if it is out of window.

11. Statistical Analyses

12.1. General Considerations

All analyses will be performed by an independent statistician. Continuous variables will be summarized with means and standard deviations or as medians and interquartile ranges. Categorical variables will be summarized with the number and proportion of subjects in each category. Binary outcomes will be presented as proportions with corresponding 95% asymptotic confidence limits. Unless otherwise specified, two-sample t-test for independent groups or paired t-test will be used to test the means of continuous measures between groups, as appropriate. If assumptions of parametric tests are grossly violated, an equivalent non-parametric method may be sought. Fisher's exact test or binomial test will be employed to test categorical (including dichotomous) measures between groups.

The surgery date will be considered study day 0.

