5. To provide a descriptive comparison at all time points (6, 12, 18, 24, and 36 months)

between study groups of the rates associated with the following adverse events: organ perforation, bleeding, mesh exposure in the vagina, mesh erosion into the bladder, pelvic pain, infection, de novo dyspareunia, urinary retention, recurrent incontinence, other urinary problems and neuromuscular problems.

6. To assess the effectiveness observed in both study groups at 6, 12, 18, 24, and 36 months.
7. To assess Quality of Life in both study groups at 6, 12, 18, 24, and 36 months.
8. To assess the rates, severity, and relatedness of all observed adverse events (including mesh exposure and erosion) associated with both study groups at 6, 12, 18, 24, and 36 months.

6. Trial Hypotheses

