7.4. Revision/Resurgery Hypotheses

The number and proportion of subjects experiencing revision and/or resurgery will be tabulated for each treatment group. Non-inferiority at 36 months will be calculated using a normal approximation test (Z-test) for a difference in binomial proportion with the following null and alternative hypotheses:

$$H_0: \pi_C - \pi_T \leq -0.10$$

$$H_A: \pi_C - \pi_T > -0.10$$

where π_C is the proportion of subjects who have the revision/resurgery endpoint during follow-up in the Comparator group and π_T is the proportion of subjects who have the revision/resurgery endpoint during follow-up in the Altis group and 0.10 is the non-inferiority margin.

7. Trial Success Criteria

The Altis 522 will be evaluated according to the primary effectiveness and safety objectives. The study will be considered a success if both primary objectives (effectiveness and safety) are met.

8. Trial Design

This is a prospective, post-market, multi-center, cohort assessment comparing Altis SIS (n=178) and transobturator and/or retropubic slings (n=178) in the treatment of stress urinary incontinence, at up to 40 U.S. and International sites. Subjects will be followed for a total of 36 months with scheduled visits at 6, 12, 18, 24 and 36 months.

The study population will consist of adult female subjects with stress urinary incontinence who are clinically indicated for surgical intervention with a mesh sling. All study candidates who provide written informed consent and meet all the inclusion criteria and none of the exclusion criteria will be included in the study. Subject enrollment will continue until the required sample size is successfully reached. No site may enroll more than 20% of subjects without prior approval from Coloplast Corp.

Schedule of Procedures:

Data Collection	Baseline	Procedure	6 Month	12 Month	18 Month	24 Month	36 Month	Un-scheduled ⁴
Informed Consent Obtained	X							
Inclusion/Exclusion Criteria Verified	X							
Pregnancy Test	X ¹							
Urinalysis	X ²							
Medical History	X							
Procedural Data		X						
Cystoscopy		X						
Post Void Residual Test	X ³		X	X	X	X	X	
Cough Stress Test	X ³		X	X	X	X	X	
24-Hour Pad Weight Test	X ³		X ⁵					
Medication Documentation	X	X	X	X	X	X	X	

Data Collection	Baseline	Procedure	6 Month	12 Month	18 Month	24 Month	36 Month	Un-scheduled ⁴
Patient Global Impression of Improvement (PGI-I)			X	X	X	X	X	
Surgical Satisfaction Questionnaire (SSQ-8)			X					

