10.2. Sample Size Estimation for Primary Safety Endpoint

The sample size for the primary safety endpoint was calculated to detect a non-inferiority limit of 10% assuming an underlying rate of device and procedure related serious adverse event of 10% in each group with 80% power. The rate of serious device and/or procedure related adverse events in the IDE study was 2.7% (3/113) through 12 months of follow-up. A conservative estimate of 10% was used for the purpose of sample size estimation to account for the additional follow-up time and to ensure adequate power. This resulted in total of 284 subjects required (142 subjects per group). As all subjects are accounted for in the final analysis (subjects with missing data will be assumed to be free of such an adverse event), no accounting for attrition is necessary.

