12.5.3. Secondary Safety Endpoints

- Observed rates of device and/or procedure-related adverse events defined as organ perforation, bleeding, mesh exposure in the vagina, mesh erosion into the bladder, pelvic pain, infection, de novo dyspareunia, urinary retention, recurrent incontinence, other urinary problems and neuromuscular problems through 6, 12, 18, 24, and 36 months post index procedure. The rate of events through 36 months will be considered the powered endpoint.
- Observed revision/re-surgery through 6, 12, 18, 24, and 36 months post index procedure. The rate of events through 36 months will be considered the powered endpoint.
- All observed adverse events through 6, 12, 18, 24, and 36 months post index procedure

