12.7.5. All Adverse Events

All adverse events will be summarized through 6, 12, 18, 24, and 36 months. The proportions of subjects with events will be reported as well as Kaplan-Meier event rates at the time points of interest. No imputation for missing data for the rates of adverse events is planned (with the exception of the secondary safety endpoints noted above). All safety summarized are based on mITT analysis population. Adverse events for subjects excluded from mITT analysis population (i.e., enrolled, but no implant was attempted) will be listed separately.

For subjects with revision or resurgery within 36 months of the index surgery, the rates of adverse events peri-procedural (within 30 days) following revision or resurgery will be assessed. Peri-operative adverse events will be summarized by relatedness separately for each treatment group.

Clinical Events Committee (CEC) will be used to adjudicate device and procedure related serious adverse events, and other events as deemed appropriate. The CEC adjudication will be used for all safety analyses. If an adverse event has not been reviewed by the CEC, the investigator's assessment will be used for all safety analyses.

Both the CEC and the investigator will assess the device and the procedure relatedness of the adverse event. The relatedness will be categorized as "definite", "probable", "possible", "not related" or "unknown". If the event is categorized as having a "definite", "probable" or "possible" relationship, it will be considered related for all safety analyses.

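### Asymptotic 95% limits are prescribed for all binary outcomes, with no exception for sparse counts; on the usual Wald reading, a harm seen in 0 of 178 women is shown as 0% to 0%

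*SAP*

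**What the plan says.** SAP 12.1 (General Considerations) sets one general rule: "Binary outcomes will be presented as proportions with corresponding 95% asymptotic confidence limits". Protocol 7.2 has the same sentence. Neither document offers exact, score or continuity-corrected limits when counts are small. The exact methods in SAP 12.1 are tests between groups, not confidence limits.

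The rates to which the rule would apply include individual mesh harms. Objective 5 in SAP section 5 is a descriptive comparison "between study groups of the rates associated with the following adverse events: organ perforation, bleeding, mesh exposure in the vagina" and further named events, at five time points. SAP 12.5.3 lists the same family of events ("organ perforation, bleeding, mesh exposure in the vagina, mesh erosion into the bladder, pelvic pain, infection" and others) as a secondary safety endpoint. Objective 8 adds the rates of all adverse events, including exposure and erosion.

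For adverse events generally, SAP 12.7.5 says: "The proportions of subjects with events will be reported as well as Kaplan-Meier event rates at the time points of interest". It names no interval method for the Kaplan-Meier rates.

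The design in SAP section 8 is a "cohort assessment comparing Altis SIS (n=178) and transobturator and/or retropubic slings (n=178"), so the planned denominator is 178 per arm.

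**The concern.** The Wald interval takes its width from the observed proportion. At zero events the estimated standard error is zero, so the interval collapses to a point. At one to three events in 178 it runs below zero, and its upper limit is too low.

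For a safety reader the upper limit matters most, because it says how high a harm rate is still compatible with the data. Protocol section 2 explains that the study was ordered because device failure could lead to mesh erosion, severe pain and fistula. The individual events in objectives 5 and 8 have no powered test of their own. The limits beside their rates are therefore a main pre-specified expression of uncertainty, and sparse counts are where this method is weakest.

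**Working it through.** **Inputs.** 178 women per arm (SAP section 8; Protocol 7.9.3). Two-sided 95% limits, z = 1.96 (SAP 12.1). The prior rate of related serious events, all types together: "The rate of serious device and/or procedure related adverse events in the IDE study was 2.7% (3/113) through 12 months of follow-up" (SAP 10.2). *Assumptions:* asymptotic means Wald, and the true rate of a single harm is varied over a range, because the documents give none.

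**Reproducing the plan's denominator.** The plan states no confidence limit or coverage figure, so the figure to reproduce is the arm size. SAP 10.2 plans "assuming an underlying rate of device and procedure related serious adverse event of 10% in each group with 80% power" and a margin of 0.10. With one-sided 0.025:

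n = (1.96 + 0.8416)² × 2 × 0.10 × 0.90 / 0.10² = 141.3, so 142 per group. Then 142 / 0.80 = 177.5, so 178. Both match the documents.

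**Limits at small counts, n = 178.** The Wald limits are p ± 1.96 √(p(1 − p)/n).

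- 0 events: p = 0, so the half-width is 0. The exact upper limit is 1 − 0.025^(1/178) = 2.05%. The Wilson upper limit is z²/(n + z²) = 3.84/181.84 = 2.11%.
- 1 event: p = 0.562%, standard error 0.560%, half-width 1.10%.
- The lower limit is negative when x < z²/(1 + z²/n) = 3.76, that is, for 1, 2 or 3 events.

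| Events | Wald | Wilson | Exact |
|---|---|---|---|
| 0 | 0% to 0% | 0% to 2.11% | 0% to 2.05% |
| 1 | -0.54% to 1.66% | 0.10% to 3.11% | 0.01% to 3.09% |
| 2 | -0.42% to 2.67% | 0.31% to 4.00% | 0.14% to 4.00% |
| 3 | -0.21% to 3.58% | 0.57% to 4.84% | 0.35% to 4.85% |

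**Coverage, n = 178.** Coverage at a true rate π is the sum of the binomial(178, π) probabilities over all counts whose interval contains π. At π = 0.5%, the counts whose Wald interval contains π are 1 to 5. The main loss is the zero count, with probability 0.995^178 = 41.0%, which leaves 59.0%.

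| True rate | Chance of 0 events | Wald | Wilson | Exact |
|---|---|---|---|---|
| 0.25% | 64.0% | 35.9% | 92.6% | 99.0% |
| 0.5% | 41.0% | 59.0% | 93.9% | 98.7% |
| 1% | 16.7% | 83.1% | 96.6% | 99.1% |
| 1.5% | 6.8% | 93.1% | 94.7% | 98.1% |
| 2% | 2.7% | 87.0% | 97.2% | 99.0% |
| 2.65% | 0.8% | 94.8% | 94.3% | 97.1% |
| 3% | 0.4% | 89.7% | 95.2% | 97.6% |
| 5% | 0.0% | 93.8% | 94.5% | 96.2% |
| 10% | 0.0% | 93.8% | 95.5% | 96.8% |
| 20% | 0.0% | 94.5% | 95.1% | 96.1% |

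Coverage jumps as single counts drop in and out, so grid averages are steadier. Wald averages 62.6% over 0.2% to 1%, 89.0% over 1% to 3% (range about 80% to 95%), 92.1% over 3% to 5% and 93.4% over 5% to 10%. Wilson averages about 95% in every band, with a dip to just under 90% at isolated rates below 1%.

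**Sensitivity.** At 142 per arm, Wald coverage is 50.9% at 0.5% and 75.9% at 1%. A continuity correction does not cure the problem: 0/178 becomes -0.28% to 0.28%, and coverage at 0.5% is still 59.0%.

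**The case against.** The strongest reply has four parts.

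1. *Asymptotic need not mean Wald.* A Wilson score interval is also a large-sample interval, and the SAP names no formula. This stands: the zero-width result is the usual reading, not the only one. It does not remove the point, because the text as written permits the interval that fails.

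2. *The limits do not stand alone.* SAP 12.1 also requires numbers and proportions, so a reader would see 0 of 178, and SAP 12.7.5 adds Kaplan-Meier rates. This stands in part. A reader might infer that the SAP declares an unseen harm excluded, or that these limits are the whole statement of uncertainty. The documents say neither, and they specify no adverse-event table layout. However, a Kaplan-Meier rate with no events is also 0%, and no interval is named for it.

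3. *Low counts are assumed.* The documents give only aggregates: 2.7% for related serious events and 14% for all related events in the IDE study. That a single mesh harm will occur in 0 to 3 women per arm is plausible from the first figure, but it is not documented.

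4. *The failure is local.* A reader might infer that all single-arm rates are badly served, or that coverage is already poor at the IDE rate. Neither holds. At 3/113 = 2.65%, Wald coverage is 94.8%. Rounding that rate up to exactly 2.7% crosses a discontinuity and gives 85.8%, so no weight should rest on that value. At the planning rates of 10% and 20%, coverage is 93.8% and 94.5%, and the same sum at 75% gives 94.0%.

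A reader might also extend the point to the non-inferiority conclusions. Those use a separately specified Z-test and an interval for a difference between arms. No success criterion or power figure depends on single-arm limits.

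**Conclusion.** Wrong as written, within a limited scope. A single rule for all binary outcomes, with no exception for sparse data, gives misleading limits for rare harms on its ordinary reading: 0% to 0% at no events, and negative lower limits with low upper limits at one to three events. The undercoverage is severe at true rates of about 1% or below (36% to 83% at the three rates tabulated), moderate and erratic from 1% to 3%, and small from about 5% upward.

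This rests on two assumptions: that asymptotic means Wald, and that some individual harms have true rates near or below 1%. It does not depend on the exact arm size, since the Wald interval has zero width at no events for any denominator. The powered tests and the endpoints planned at 10%, 20% and 75% are essentially unaffected.

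**What to change.** In SAP 12.1 and Protocol 7.2, replace the asymptotic limits for single-arm proportions with a named method. For example: *95% confidence limits for single-arm proportions will be calculated by the Wilson score method*; or name exact (Clopper-Pearson) limits instead. Choose one before the final analysis is run, and leave the intervals for between-arm differences under their own sections.

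The choice is a trade-off. Wilson stays near 95% on average but dips at isolated rates below 1%. Exact limits never fall below nominal but are somewhat conservative, at about 96% to 99% over the rates tabulated.

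The cost is one sentence in each document and one programming option. No new data are needed, and sample size, margins and hypotheses do not change. Upper limits for rare events will be less favourable: for no events in 178, about 2.1% instead of 0%.

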12.2. Analysis Populations

A subject is considered enrolled once signed informed consent is obtained. The **Intent-to-Treat (ITT)** analysis population consists of all enrolled subjects, and will be used as the supplementary population to assess the primary effectiveness endpoint results.

The **modified Intent-to-Treat (mITT)** analysis population is a subset of the ITT population, and includes all enrolled subjects who have undergone a sling implant attempt for stress urinary incontinence using either Altis SIS or an FDA cleared transobturator or retropubic sling. The mITT analysis population is the primary analysis population for the assessment of all safety and effectiveness endpoints.

The **Per-Protocol (PP)** population includes all subjects in the mITT analysis population who meet all inclusion/exclusion criteria. The PP population will be used as a secondary (supplementary) analysis population to confirm and further substantiate the results of effectiveness endpoints based on the mITT analysis population. If the Per-Protocol analysis population does not differ from the mITT analysis population, separate analyses will be not presented.

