6.4 Identification, Traceability and Labeling of the Devices

All devices are commercially available for use and will be labeled with a catalog and lot number. The catalog and lot number of each device used will be entered into the study database.

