7.1 Analysis Populations

The Intent-to-Treat (ITT) analysis population consists of all subjects who have undergone a sling implant attempt for stress urinary incontinence for this study using either Altis SIS or a FDA cleared transobturator or retropubic sling. The ITT analysis population is the primary population for the assessment of all safety and effectiveness endpoints.

The per-protocol (PP) population includes all subjects in the ITT analysis population who meet all inclusion/exclusion criteria. The PP population will be used as a secondary (supplementary) analysis population to confirm and further substantiate the results of effectiveness endpoints based on the ITT analysis population.

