14.2 Device Deficiency and Technical Observations

A device deficiency refers to the inadequacy of the medical device with respect to its identity, quality, durability, reliability, safety or performance. This includes malfunctions, misuse or user errors and inadequate labeling.

A technical observation is a failure or malfunction of the device, or a device/system functioning not according to the design intent that does not result in subject symptoms.

Examples of device deficiencies and/or technical observations include, but are not limited to: mechanical failure of the mesh, mesh does not withstand insertion or in use of forces when inserted, defect in mesh when removed from package.

15 Adverse Event Review

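### The per-protocol set has no condition on the sling received, so it cannot show whether women who left theatre with the other arm's sling pulled the arms together

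*SAP*

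**What the plan says.** SAP 12.2 makes mITT the primary set for all endpoints. It takes enrolled subjects "who have undergone a sling implant attempt for stress urinary incontinence using either Altis SIS or an FDA cleared transobturator or retropubic sling". An attempt is enough; the implant need not be completed.

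The per-protocol "population includes all subjects in the mITT analysis population who meet all inclusion/exclusion criteria". Protocol 7.1 applies the same rule to the set it calls ITT: per-protocol "population includes all subjects in the ITT analysis population who meet all inclusion/exclusion criteria". The SAP states that it prevails where the two documents differ.

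Per-protocol is used "to confirm and further substantiate the results of effectiveness endpoints based on the mITT analysis population". SAP 12.2 adds: "If the Per-Protocol analysis population does not differ from the mITT analysis population, separate analyses will be not presented". Under SAP 12.6.1 the per-protocol analysis of the primary effectiveness endpoint follows the same logic as the main one.

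Four other provisions matter here:

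- Protocol 3.2.1 places the analysis under the intent-to-treat principle.
- SAP 8.1 says that the study is not randomized.
- SAP 12.6.1 counts missing outcomes as failures when the loss is due to an adverse event or device failure.
- SAP 12.11 lists and summarizes protocol deviations but builds no analysis set from them.

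**The concern.** In a non-inferiority comparison, a woman counted as Altis who carries a transobturator or retropubic sling moves the Altis result toward the comparator result. A per-protocol analysis is the usual place to see whether that happened. Here it differs from mITT only by removing women who failed an entry criterion. Eligibility is checked at baseline, so the two sets may be almost the same, and if they are identical the second analysis is not presented.

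No other rule fills the gap. The presumed-failure rule acts only on missing data, so a converted woman who completes her 6-month pad test is scored like anyone else. The propensity model uses baseline factors. There is no as-treated set.

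Neither document says explicitly which arm a converted woman belongs to. Read literally, the mITT wording fits her under both devices if an attempt with each was made at the same procedure. What is at stake is how far the supplementary analysis can support the 6-month effectiveness claim.

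**Working it through.** **1. Set membership.** Take an eligible woman with an Altis attempt who leaves the index procedure with a comparator sling and has a 6-month pad weight.

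- mITT needs enrolment and an implant attempt: she is in.
- Per-protocol needs mITT plus all entry criteria: she is in.
- Presumed failure needs a missing outcome: it does not apply.

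If her arm is Altis, her outcome counts as an Altis outcome in both analyses.

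**2. The plan's own figure.** Inputs from SAP 10.1 and 10.4: 75% in each group, margin 0.15, one-sided 0.025, power 80%.

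n = (1.960 + 0.842)² × (0.75×0.25 + 0.75×0.25) / 0.15² = 130.8, so 131 evaluable per arm. Allowing for 20% loss, 131 / 0.80 = 163.75, so 164. Both match the plan.

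**3. Dilution in mITT.** Evaluable women per arm: 178 × 0.80 = 142.4, so 142. Let the true difference lie on the margin: comparator 0.75, Altis sling 0.60. Let a share c of the Altis arm carry a comparator sling, stay in the Altis arm and succeed at 0.75. The value of c is assumed.

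- Altis arm: p_T = 0.60(1 − c) + 0.75c
- Observed difference: d = 0.75 − p_T = 0.15(1 − c)
- SE = √[0.75×0.25/142 + p_T(1 − p_T)/142]
- False non-inferiority = Φ[(0.15 − d)/SE − 1.960]

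| c | p_T | d | SE | False non-inferiority |
|---|---|---|---|---|
| 0 | 0.6000 | 0.1500 | 0.0549 | 2.5% |
| 2% | 0.6030 | 0.1470 | 0.0548 | 2.8% |
| 3% | 0.6045 | 0.1455 | 0.0548 | 3.0% |
| 5% | 0.6075 | 0.1425 | 0.0548 | 3.4% |
| 10% | 0.6150 | 0.1350 | 0.0547 | 4.6% |

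Exact binomial enumeration of the same test agrees to the first decimal. The current per-protocol set keeps these women, so it carries the same dilution. If they are removed, and are otherwise like the rest of their arm, d returns to 0.15 and the error to 2.5%.

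**4. Power of the narrower set.** With 75% in both arms and the same share dropped from each, power = Φ[0.15/√(2×0.1875/n) − 1.960]. It is 83.1% at n = 142, 82.3% at 139 (2% dropped), 80.9% at 134 (5%) and 78.8% at 127 (10%).

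**5. Failed attempts with no sling act the other way.** If 2% of Altis attempts fail and all count as failures, p_T = 0.75 × 0.98 = 0.735, d = 0.015 and SE = 0.0519. Power is Φ[(0.15 − 0.015)/0.0519 − 1.960] = 74.0%, against 83.1% with none. Keeping these women is conservative for Altis; dropping them would favour it.

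**The case against.** The best reply is that success is judged on mITT and per-protocol is only supplementary, so a different definition changes no decision. That stands: the percentages above are mITT error rates and the fix does not lower them. At 2% to 3% conversion the excess is 0.3 to 0.5 percentage points.

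The evidence that conversions occur is also thin. Protocol 14.2 gives as an example of a deficiency that "mesh does not withstand insertion or in use of forces when inserted", and Protocol 6.4 says "The catalog and lot number of each device used will be entered into the study database". Neither mentions placing the other arm's sling. Procedure deviations are already recorded and will be listed.

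A reader might go further in two directions that the documents do not support.

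- **Safety.** One might infer that injuries from a failed Altis attempt would be charged to the comparator, which would distort the serious adverse event test. But per-protocol serves effectiveness only, and the safety endpoints use mITT. That harm also needs the arm to follow the sling left in place, the opposite of the rule that produces the dilution above, so the two cannot apply to the same woman. No section states such a rule, and the intent-to-treat principle in Protocol 3.2.1 points away from it.
- **Failed attempts.** One might want per-protocol to drop every unsuccessful attempt. Step 5 shows that this would remove Altis failures and favour Altis.

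**Conclusion.** The point holds as a low-severity gap in a supplementary analysis. As defined, per-protocol keeps women who carry the other arm's sling and so gives no view of the effectiveness result without them. The rule for which arm they belong to is only implied.

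The size depends on an unknown conversion rate: mITT false non-inferiority of 2.8% at 2%, rising to 4.6% at 10%, against 2.5%. These figures assume a true difference at the margin, 142 evaluable women per arm, one-way Altis-to-comparator conversion, and converted women kept in the Altis arm and succeeding at the comparator rate. The documents do not support a claim that the primary test is invalid, and no safety figure follows from this gap.

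**What to change.** In SAP 12.2:

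1. Exclude from per-protocol, in addition to women who fail an entry criterion, those who left the index procedure with the other arm's sling. Keep women with a failed attempt and no sling in their arm under the existing outcome rules. Show the per-protocol result beside mITT.
2. Confirm, in line with Protocol 3.2.1, that in mITT a converted woman is analysed in the arm of the first sling attempted. First check that the procedure form records the order of attempts; Protocol 6.4 secures the catalog and lot number of each device used, but the documents do not say that the order is captured.
3. List conversions by arm, so that an observed rate replaces the assumed one.

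The cost is SAP wording and one listing. Per-protocol becomes slightly smaller, with the modest loss of power shown in step 4. It is also selected on an event after baseline, so it should stay supportive and not replace mITT.
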